11.6. Ibrutinib adverse events of special interest

Hemorrhagic Adverse Events

Fatal bleeding events have occurred in patients treated with ibrutinib. Grade 3 or higher bleeding events (subdural hematoma, gastrointestinal bleeding, hematuria and post procedural hemorrhage) have occurred in up to 6% of patients. Bleeding events of any grade, including bruising and petechiae, occurred in approximately half of patients treated with ibrutinib. The mechanism for the bleeding events is not well understood. Ibrutinib may increase the risk of hemorrhage in patients receiving antiplatelet or anticoagulant therapies.

Subjects in the current study will be monitored closely for hemorrhagic adverse events. Ibrutinib should be held at least 3 to 7 days pre and post-surgery depending upon the type of surgery and the risk of bleeding (please refer to Section 9.7 for further details).

Infection

Fatal and non-fatal infections have occurred with ibrutinib therapy. Grade 3 or greater infections occurred in 14% to 29% of patients. Cases of progressive multifocal leukoencephalopathy (PML) have occurred in patients treated with ibrutinib. Monitor patients for fever and infections and evaluate promptly.

Cytopenias

Treatment-emergent Grade 3 or 4 cytopenias including neutropenia (range, 19 to 29%), thrombocytopenia (range, 5 to 17%), and anemia (range, 0 to 9%) occurred in patients treated with ibrutinib. Monitor complete blood counts monthly.

Atrial Fibrillation

Atrial fibrillation and atrial flutter (range, 6 to 9%) have occurred in patients treated with ibrutinib, particularly in patients with cardiac risk factors, acute infections, and a previous history of atrial fibrillation. Periodically monitor patients clinically for atrial fibrillation. Patients who develop arrhythmic symptoms (e.g., palpitations, lightheadedness) or new onset dyspnea should have an ECG performed. If atrial fibrillation persists, consider the risks and benefits of ibrutinib treatment and dose modification based on recommendations in Section 9.

Hypertension

Hypertension (range, 6 to 17%) has occurred in patients treated with ibrutinib with a median time to onset of 4.6 months (range, 0.03 to 22 months). Monitor patients for new onset hypertension or hypertension that is not adequately controlled after starting ibrutinib. Adjust existing anti-hypertensive medications and/or initiate anti-hypertensive treatment as appropriate.

Secondary Primary Malignancies

Other malignancies (range, 5 to 16%) including non-skin carcinomas (range, 1 to 4%) have occurred in patients treated with ibrutinib. The most frequent second primary malignancy was non-melanoma skin cancer (range, 4 to 13%).

Tumor Lysis Syndrome

Tumor lysis syndrome has been reported with ibrutinib therapy. Assess the baseline risk (e.g. high tumor burden) and take appropriate precautions. Monitor patients closely and treat as appropriate.

Embryo-Fetal Toxicity

Based on findings in animals, ibrutinib can cause fetal harm when administered to a pregnant woman. Administration of ibrutinib to pregnant rats and rabbits during the period of organogenesis caused embryofetal toxicity including malformations at exposures that were 2-20 times higher than those reported in patients with MCL, CLL/SLL or WM. Advise women to avoid becoming pregnant while taking ibrutinib and for 1 month after cessation of therapy. If this drug is used during pregnancy or if the patient becomes pregnant while taking this drug, the patient should be apprised of the potential hazard to a fetus.

11.7. Copanlisib anticipated toxicities

The side effects listed below have been reported by patients who have received copanlisib in clinical trials

Likely (>20%): Anemia, hyperglycemia, hypertension, fatigue, nausea, diarrhea, neutropenia (including febrile neutropenia), infections, rash (including macular, maculopapular, pruritic, pustular, erythematous, generalized, exfoliative rash, pruritus/Pruritus generalized, dermatitis acneiform, dermatitis allergic and dermatitis exfoliative)

Less Likely (4-20%): Dysgeusia, leukopenia, lymphopenia, elevated amylase and lipase increased, hypomagnesemia, hyponatremia, paraesthesia, pneumonitis, interstitial lung disease, thrombocytopenia, vomiting, chills, mucosal inflammation (including stomatitis and mouth ulceration), dry mouth, muscle spasms

Rarely (<3%): alopecia, hyperinsulinemia, infusion related reaction, hypersensitivity, gastritis, colitis, aphthous ulcer, eosinophilia, Pancreatitis, Stevens-Johnson syndrome

Most side effects listed above have been mild to moderate in severity; however severe side effects have occurred. Some side effects have been severe enough to lead to study drug discontinuation, dose modification or reduction, hospitalization, disability and sometimes death.

11.8. Copanlisib adverse events of special interest

Non-Infectious Pneumonitis

Non-infectious pneumonitis is an adverse event of special interest. In general, non-infectious pneumonitis was symptomatic, with fever, cough, and dyspnea but asymptomatic in some patients. Therefore CT scans may be used to assess for radiographic indications of non-infectious pneumonitis. The CT findings in case of non-infectious pneumonitis were diffuse ground-glass opacities. A bronchoscopy may not show any findings. Non-infectious pneumonitis resolved in all 9 patients, usually within 2 to 4 weeks. No patient died due to non-infectious pneumonitis. In all 9 patients, study drug was interrupted and in 3 patients permanently discontinued due to non-infectious pneumonitis. Interruption of study drug alone improved non-infectious pneumonitis in 1 patient, 1 patient received steroids only, 2 patients received antibiotics only, and 6 patients received antibiotics and steroids. Re-treatment with study drugs was performed in 2 patients, resulting in re-occurrence of non-infectious pneumonitis in 1 of them.

Hyperglycemia

The PI3K/AKT pathway plays a significant role in regulating glucose metabolism. Hyperglycemia is considered as an “on target” effect of copanlisib, and has been commonly observed in patients treated with copanlisib with an incidence approximately 50-70%.

Hypertension

Approximately 42% of patients have post infusion drug related Grade 3 hypertension. There were no cases of Grade 4 hypertension. There was a CTC Grade 3 SAE hypertension. Hypertension was reported in the medical history of 22 out of 76 patients; 16 of them were already receiving antihypertensive treatment at study start. Antihypertensive treatment was administered in 8 treatment naive patients as a consequence of post infusion hypertension, and in 7 patients due to a worsening of already therapy controlled baseline hypertension. Six of the eight naive patients received treatment only on the day of infusion, and 2 naive patients started chronic antihypertensive treatment.

12.0 CRITERIA FOR THERAPEUTIC RESPONSE/OUTCOME ASSESSMENT

Response and progression of disease will be evaluated in this study using the RECIL criteria[37]. Clinical evaluation and tumor assessments will be performed periodically, as is indicated in Table 10-1, based on physical examination, radiological evaluation and core bone marrow biopsy (in patients

with pre-existing bone marrow involvement). Clinical suspicion of disease progression at any time will require a physical examination and radiological confirmation to be performed promptly, rather than waiting for the next scheduled tumor assessment. In case of an unscheduled or delayed tumor assessment for any reason, subsequent tumor assessments must be performed according to the originally planned schedule from baseline.

Measurability of lesion for objective response and measurement of target lesions: Measurable disease: lesions that can be accurately measured in two dimensions by CT, MRI, plain x-ray or other conventional technique and have a greatest transverse diameter of 1.5 cm or greater. Non-measurable disease: All other lesions including uni dimensional lesions, lesions too small to be considered measurable, pleural or pericardial effusions, ascites, bone disease, leptomeningeal disease, lymphangitis, pulmonitis, abdominal masses not confirmed by CT, or disease documented only by indirect evidence (e.g. lab values).

Assessment of tumor burden in lymphoma clinical trials can use the sum of longest diameters (SLD). In patients with disseminated disease, a maximum of three target lesions should be selected and used to estimate tumor response. Target lesions should be selected from those with the largest size that can be reproducibly measured and preferably representing multiple sites and/organs. In most cases, lymph nodes can be considered target lesions if the lymph node longest diameter measures ≥ 15 mm. Similar to RECIST 1.1, a lymph node measuring between 10 and 14 mm is considered abnormal but should not be selected as a target lesion. Lymph nodes measuring <10 mm in diameter are considered normal. In certain anatomical sites (inguinal, axillary, and portocaval), normal lymph nodes may exist in a narrow, elongated form, and such nodes should not be selected as target lesions if alternatives are available. Extranodal lesions are selected as target lesions if they have soft tissue component, based on their size, and the ease of reproducibility of repeated measurements, with a minimum measurement of the longest diameter of ≥ 15 mm. All other lesions should be identified as nontarget lesions and should be recorded at baseline, without the need to measure them. Nontarget lesions should be followed and reported as present, absent, or clear progression.

Objective disease response assessment: Objective status is to be recorded at each evaluation according to the RECIL criteria

Table 12-1. Criteria for RECIL Response Assessment of Non-Hodgkin Lymphoma

13.0 CRITERIA FOR REMOVAL FROM STUDY

Patients may voluntarily withdraw from the study or be removed from the study at the discretion of the investigator at any time. Patients may be withdrawn from the study if any of the following occur:

- Disease progression. However, if progression develops after CR while patient is on ibrutinib alone, patients could restart treatment upon radiographic and pathologic expression of disease.
- Ineligibility (at the pretreatment evaluation) of the patient as defined in the inclusion/ exclusion criteria
- Treatment will be discontinued at the request of the patient, refusal of therapy, non-compliance, or upon the development of an intercurrent significant medical illness.
- Significant protocol violation
- Unacceptable toxicity
 - Grade 4 arterial hypertension
 - Grade 4 dermatologic toxicity
 - Non-infectious pneumonitis
 - Drug induced clinically relevant pancreatitis
 - Grade ≥ 3 hypersensitivity reaction
- Decision by the investigator that termination is in the patient's best medical interest.
- Loss to follow-up

- Development of active HBV or HCV infection, hepatitis, or HIV infection
- Pregnancy or a positive pregnancy test
- Death of the patient

In addition to the general study treatment withdrawal criteria, the following study specific criteria will also require premature study treatment discontinuation:

- Use of prohibited medication
- Start of any other anti-neoplastic therapy

If a study treatment withdrawal occurs, or if the patient fails to return for visits, the investigator must determine the primary reason for a patient's premature withdrawal from study treatment and record this information on the End of Treatment CRF page.

14.0 BIOSTATISTICS

14.1. Phase I

In the Phase I part the standard 3+3 dose escalation scheme will be used. If none of the initial cohort of 3 has a DLT (defined in Section 9.2) the dose level will be escalated. If one has a DLT that dose level will be expanded with 3 more patients. Dose escalation will stop if 2 or more DLTs are seen at a dose level within the treatment and observation periods as described in Section 9.2. The MTD is defined as the highest dose level at which at most 1 of the 6 patients treated at that level has a DLT. Two dose levels plus a "-1" dose level are planned for this study. The maximum sample size is 18 patients. Toxicity seen after 4 weeks that are likely or definitely related to treatment with study drugs will be collected and evaluated by the investigators.

All patients that stop protocol therapy or have dose reductions due to a DLT will be included in the DLT analysis. If a patient stopped therapy for other reasons and has taken $\leq 75\%$ of planned doses (2 of 3 copanlisib doses and 21 of 28 doses of ibrutinib) in the first cycle then they will be excluded from DLT analysis. In the event that a patient withdraws from the trial due to a reason unrelated to a DLT before completing cycle one, they will be replaced. We expect that less than 10% of patients will be replaced due to insufficient time of treatment. The probability of dose escalation based on various underlying DLT rates (Table 2).

Table 14-1. DLT probability table								
True DLT rate	5%	10%	15%	20%	25%	30%	40%	50%
Probability of escalation	0.97	0.91	0.81	0.71	0.60	0.49	0.31	0.17

It is expected that 2-3 patients will be enrolled per month and so the phase I portion of the trial will be completed in approximately 6 months.

14.2. Phase II

The primary objective for this phase II cohort is to assess the complete response rate based on best response by 6 months of ibrutinib and copanlisib and the secondary objective is to measure the disease control rate (stable disease, partial response, and complete response), overall response rate (partial and complete response), duration of response, progression and event free survival. A Simon mini-max two stage design will be used with the goal to increase by complete response rate based on best response by 6 months from 20% to 40%. In first stage, if 5 or more of 18 patients have responses, then the trial will proceed to stage 2. In stage 2, additional patients are enrolled to make the total sample size 33. If 11 or more responses are observed, then the combination is deemed promising. Accrual will not be held while the initial 18 patients in the first stage are evaluated for the 6-month response endpoint. The one sided type I error rate is 0.05 and the power is 0.80. A total of 33 patients will be enrolled, though patients treated at MTD/RP2D from phase I portion of the study will be included in the phase II analysis. Expected accrual is 2-3 patients per month and so the phase II portion will be completed within a year.

For other secondary objectives, the event free survival and progression free survival rates will be assessed by the Kaplan-Meier estimation. Event free survival is defined from the date of first dose to progression, or death, and any events including treatment discontinuation for adverse events or severe adverse events whichever came first. Progression free survival is defined from the date of first dose to progression or death, whichever came first. The duration of response will also be assessed by Kaplan-Meier method but on a sub-cohort of patients who showed any response.

To protect patients from excessive toxicity of the treatment during the entire treatment period, several stopping rules are implemented during the study based on the maximum total number of treated patients in both phase I and II (45). **Treatment related Grade ≥ 3 Pneumonitis or Colitis:** 10% unacceptable rate, 2.5% acceptable rate. Trial to hold enrollment if ≥ 4 deaths related to treatment at any point during the study. Otherwise, hold enrollment based on number of treated patients.

Number of treated patients	1	14	33	45
Number of Gr ≥ 3 Pneumonitis/Colitis to stop the trial	1	2	3	4

Operating characteristics of the early stopping rule for grade ≥ 3 treatment related pneumonitis/colitis:

True tox rate	0.025	0.04	0.055	0.07	0.085	0.1
Probability of claiming treatment too toxic	0.092	0.224	0.377	0.528	0.661	0.767

Treatment related death: 10% unacceptable rate, 2.5% acceptable rate. Trial to hold enrollment if ≥ 4 deaths related to treatment at any point during the study. Otherwise, hold enrollment based on number of treated patients.

Number of treated patients	1	14	33	45
Number of death to stop the trial	1	2	3	4

Operating characteristics of the early stopping rule for treatment related death:

True tox rate	0.025	0.04	0.055	0.07	0.085	0.1
Probability of claiming treatment too toxic	0.092	0.201	0.323	0.444	0.555	0.652

Any one Grade ≥ 3 Treatment non-hematologic Related Toxicity: 60% unacceptable rate, 40% acceptable rate. Trial to hold enrollment if ≥ 25 single toxicity event related to treatment at any point during the study. Otherwise, hold enrollment based on number of treated patients.

Number of treated patients	Number of Gr ≥ 3 non-hematologic toxicity events to stop the trial
1	1
2	2
4	4
5	5
7	6
9	7
10	8
12	9
14	10
16	11
18	12
20	13
22	14
24	15
26	16
28	17
30	18
32	19
34	20
36	21
39	22
41	23
43	24
45	25

Operating characteristics of the early stopping rule for grade ≥ 3 treatment non-hematologic related toxicity:

True tox rate	0.40	0.44	0.48	0.52	0.56	0.60
Probability of claiming treatment too toxic	0.099	0.194	0.339	0.522	0.707	0.854

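### Section 14.2 gives the pneumonitis/colitis and treatment-related-death rules one boundary but two sets of stopping probabilities, and words the pneumonitis/colitis overall trigger for deaths

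*Combined protocol and SAP*

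**What the plan says.** Section 14.2 (Phase II) sets stopping rules over a maximum of 45 treated patients across both phases. Two of them concern us.

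- **Grade ≥3 pneumonitis or colitis.** The design rates and overall trigger read "10% unacceptable rate, 2.5% acceptable rate. Trial to hold enrollment if ≥ 4 deaths related to treatment at any point during the study". Below the treated-patient counts 1, 14, 33 and 45, the boundary row reads "Number of Gr ≥ 3 Pneumonitis/Colitis to stop the trial 1 2 3 4". Under "Operating characteristics of the early stopping rule for grade ≥ 3 treatment related pneumonitis/colitis" the probabilities for true rates 0.025, 0.04, 0.055, 0.07, 0.085 and 0.10 are "0.092 0.224 0.377 0.528 0.661 0.767".
- **Treatment-related death.** The rates are given as "Treatment related death: 10% unacceptable rate, 2.5% acceptable rate", followed by the same trigger sentence. Below the same four patient counts, the boundary row reads "Number of death to stop the trial 1 2 3 4". Under "Operating characteristics of the early stopping rule for treatment related death", for the same six true rates, the figures are 0.092, 0.201, 0.323, 0.444, 0.555 and 0.652.

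The third rule, for Grade ≥3 non-hematologic toxicity, names its own event in its trigger (25 or more toxicity events).

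**The concern.** The stopping probability depends only on the boundary, the number of patients and the true event rate. The name of the event does not enter. Two rules that agree on all three must have the same row of probabilities, and these rows agree only at 2.5%. At least one row, or one boundary, is therefore not the one intended.

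This matters because one of the rules governs treatment-related death. A committee reading Section 14.2 cannot tell whether it is approving the printed boundary or a rule with the printed error rates. The stated chance of failing to stop at a true 10% death rate is 1 − 0.652 = 0.348; the pneumonitis/colitis row for the same boundary implies 1 − 0.767 = 0.233.

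Separately, the pneumonitis/colitis rule's overall trigger counts a different event from the one the rule is meant to monitor.

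**Working it through.** **Inputs (all Section 14.2).** Boundary 1/2/3/4 events at 1/14/33/45 patients; maximum 45; true rates 0.025 to 0.10; the two printed rows.

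**Reading of the table.** The text does not say how to read it. I take each listed count as the upper limit for its threshold: stop at ≥1 event at n = 1, ≥2 by n = 14, ≥3 by n = 33, ≥4 by n = 45. Events only accumulate, so checking after every patient or only at those four counts gives the same answer.

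**Method.** Carry forward the probability of k events without having stopped. With m further patients, P(k) becomes Σ P(k−j)·C(m, j)·p^j·(1−p)^(m−j). Remove the mass at or above the threshold at each look and add up what was removed.

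**Worked case, p = 0.10.**

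- n = 1: stop 0.1000; continue with 0 events, 0.9000.
- n = 14 (13 more): 0 events 0.9 × 0.9^13 = 0.2288; 1 event 0.9 × 13 × 0.1 × 0.9^12 = 0.3304; stop 0.9000 − 0.2288 − 0.3304 = 0.3408.
- n = 33 (19 more): continue with 0, 1 or 2 events at 0.0309, 0.1099, 0.1595; stop 0.2590.
- n = 45 (12 more): continue with 0, 1, 2 or 3 events at 0.0087, 0.0427, 0.0935, 0.0880; stop 0.0674.
- Never stopped: 0.0087 + 0.0427 + 0.0935 + 0.0880 = 0.2329. Stopped: 1 − 0.2329 = 0.7671.

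At p = 0.025 the four stopping steps are 0.0250 + 0.0396 + 0.0267 + 0.0053 = 0.0966.

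**All six rates.**

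| True rate | Computed | Pneumonitis/colitis, stated | Death, stated | Death: stated − computed |
|---|---|---|---|---|
| 0.025 | 0.0966 | 0.092 | 0.092 | −0.005 |
| 0.04 | 0.2239 | 0.224 | 0.201 | −0.023 |
| 0.055 | 0.3766 | 0.377 | 0.323 | −0.054 |
| 0.07 | 0.5281 | 0.528 | 0.444 | −0.084 |
| 0.085 | 0.6609 | 0.661 | 0.555 | −0.106 |
| 0.10 | 0.7671 | 0.767 | 0.652 | −0.115 |

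The pneumonitis/colitis row is reproduced to three decimals at five of six rates, which supports this reading of the table. The death row is not reproduced.

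**Other readings of the printed boundary, tried against the death row.**

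- n = 1 entry dropped: 0.080, 0.205, 0.359, 0.514, 0.650, 0.759.
- Each threshold applied from its listed count onward: 0.347 rising to 0.922.
- A single test of ≥4 in 45: 0.026, 0.105, 0.234, 0.387, 0.539, 0.671.
- Boundary cut off at 33 patients: 0.091, 0.205, 0.339, 0.473, 0.596, 0.700.

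None gives the death row. A search over other boundaries finds that stopping at 2 events within 20 patients or 3 within 27 gives 0.0923, 0.2014, 0.3233, 0.4441, 0.5550, 0.6518, which is the death row to three decimals. Its first figure is also the 0.092 that does not fit in the pneumonitis/colitis row.

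**The case against.** The strongest reply is that enrollment is held by the boundary tables, which are complete and legible; the probability rows trigger nothing. If the printed death boundary is applied, the trial stops more often at a 10% death rate than the plan states (0.767 against 0.652), and the false-stop rate at 2.5% barely moves (0.097 against 0.092). Nor does the misplaced trigger leave a gap: the pneumonitis/colitis table already reaches 4 events at 45 patients, the maximum. All of this stands and limits the practical harm, provided the printed boundary is the intended one. The document does not establish that.

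A second reply is that the result rests on an unstated reading of the table, and that first entries are not treated alike. The third rule's printed probabilities (0.099 to 0.854) come out exactly only when its n = 1 and n = 2 rows are left out; with them included I get 0.432 to 0.918. This is fair, and it makes 0.097 the least secure of the computed values. It does not rescue the death row, which fails with or without the n = 1 entry. Nor does it rescue 0.092, since dropping that entry gives 0.080.

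Third, the 2-in-20, 3-in-27 match is found by working backwards. It is not unique (adding 4 within 28 gives the same figures) and it sits badly with a maximum of 45. It suggests the figures came from another design but does not prove it.

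**Conclusion.** The point holds. The two rows cannot both describe the printed boundary, and this needs no modelling assumption beyond the two rules being identical, which Section 14.2 shows. On the reading that reproduces the pneumonitis/colitis row, the death row is too low at every rate, by 0.005 at 2.5% and by 0.115 at 10%. The stated chance of missing a 10% treatment-related death rate is about 35%; the printed boundary's is about 23%. The shared 0.092 at 2.5% should be 0.097 on that reading, a small error.

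Whether the death figures or the death boundary is wrong cannot be settled from the document. If the boundary is right, the rule is more protective than stated. If the figures are right, the printed boundary is not the intended rule.

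The pneumonitis/colitis trigger is a wording error. Its effect is limited because the table below it monitors the right event. Even so, a rule for fatal toxicity should not go forward with its boundary and its error rates in conflict.

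**What to change.** In Section 14.2:

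1. The sponsor confirms the intended treatment-related-death boundary. If it is the printed one, replace the death row with 0.097, 0.224, 0.377, 0.528, 0.661, 0.767. If the stated figures are the intended ones, print the boundary that produces them.
2. Change the first pneumonitis/colitis entry from 0.092 to 0.097, once the sponsor confirms that the n = 1 entry is active.
3. Make the pneumonitis/colitis overall trigger name its own event, patients with treatment-related Grade ≥3 pneumonitis or colitis. The rule's own table already gives 4 at 45 patients.
4. Add a sentence saying that each listed patient count is the upper limit for its threshold, if that is the intended reading.

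If the printed boundary stands, the cost is corrections to two table rows, one reworded sentence and one added sentence, with no change to sample size, data collection or conduct. If it does not, the death boundary row changes as well, and so does the point at which enrollment would be held.

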9.4. Phase II dose expansion

Patients will be enrolled at the MTD of copanlisib and ibrutinib combination. The safety events in the expansion cohorts will be reviewed on an ongoing basis by the primary investigator and several stopping rules are in place to protect patients from excessive toxicity (Section 14). Based on this review, we may adjust treating dose level to the RP2D.

Table 9-3. Phase II Simon two stage mini-max dose expansion cohorts

Disease	1 st stage	Response Needed	2 nd stage	Total Accrual
Mantle cell lymphoma	18 (include 6 patients from phase I study at MTD/RP2D)	If ≥ 5 patients with CR within 6 months, proceed to 2 nd stage	15	33 patients

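### Two of the three stopping rules in Section 14.2 have stated stopping probabilities that do not follow from their printed boundaries

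*Combined protocol and SAP*

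**What the plan says.** Section 14.2 sets three rules for holding enrollment during the whole treatment period, "based on the maximum total number of treated patients in both phase I and II (45").

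- **Pneumonitis/colitis and treatment-related death.** Both have an acceptable rate of 2.5% and an unacceptable rate of 10%. Both print the same boundary: 1, 2, 3 and 4 events at 1, 14, 33 and 45 treated patients. The text for death adds: "Trial to hold enrollment if ≥ 4 deaths related to treatment at any point during the study". Each rule has its own row of stopping probabilities at the same six true rates, one under "Operating characteristics of the early stopping rule for grade ≥ 3 treatment related pneumonitis/colitis" and one under "Operating characteristics of the early stopping rule for treatment related death".
- **Non-hematologic toxicity.** The rule reads: "Any one Grade ≥ 3 Treatment non-hematologic Related Toxicity: 60% unacceptable rate, 40% acceptable rate". Its boundary runs from 1 event in 1 patient, 2 in 2 and 4 in 4 up to 25 in 45. The stated stopping probability rises from 0.099 at 40% to 0.854 at 60%.

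Section 14.1 governs the same early patients by the 3+3 scheme: "If one has a DLT that dose level will be expanded with 3 more patients".

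**The concern.** One boundary at one set of true rates has only one set of stopping probabilities. Section 14.2 gives two, so either the death boundary or the death row is wrong, and a reader cannot tell which was approved.

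The non-hematologic table matters more in practice because staff will act on it. Read literally, one related Grade ≥ 3 non-hematologic event in the first patient holds enrollment. Section 14.1 responds to one DLT in a cohort of three by adding three patients, and Section 9.2 does not count some short Grade ≥ 3 events as DLTs at all. Section 11.8 says of copanlisib: "Approximately 42% of patients have post infusion drug related Grade 3 hypertension". If that rate carried over to the combination, which is an assumption, the first patient alone would trigger a hold about 42% of the time.

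**Working it through.** **Inputs (Section 14.2).** Maximum N = 45, the three boundaries, and the six true rates printed for each rule.

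**Method.** Let f(n, k) be the probability that the trial is still open after n patients with k events. Then f(n, k) = (1 − p)·f(n−1, k) + p·f(n−1, k−1), and any state at or above the printed threshold is removed and counted as a stop. Applying each threshold up to its printed n, or checking only at the printed n, gives the same answer.

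**1. Boundary 1/1, 2/14, 3/33, 4/45 (pneumonitis/colitis and death)**

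| True rate | 0.025 | 0.04 | 0.055 | 0.07 | 0.085 | 0.10 |
|---|---|---|---|---|---|---|
| Computed | 0.097 | 0.224 | 0.377 | 0.528 | 0.661 | 0.767 |
| Stated, pneumonitis/colitis | 0.092 | 0.224 | 0.377 | 0.528 | 0.661 | 0.767 |
| Stated, death | 0.092 | 0.201 | 0.323 | 0.444 | 0.555 | 0.652 |
| Computed, without 1/1 | 0.080 | 0.205 | 0.359 | 0.514 | 0.650 | 0.759 |

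The pneumonitis/colitis row is reproduced in five of six cells, and only with its 1/1 row active. Its first cell repeats the death-row value.

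Hand check at 10%, by segment:
- Patient 1: 0.100.
- Patients 2–14: 0.9 × P(Bin(13, 0.1) ≥ 2) = 0.9 × 0.3787 = 0.341. This leaves 0.2288 with no events and 0.3304 with one.
- Patients 15–33: 0.2288 × P(Bin(19, 0.1) ≥ 3) + 0.3304 × P(Bin(19, 0.1) ≥ 2) = 0.2288 × 0.2946 + 0.3304 × 0.5797 = 0.259. This leaves 0.0309, 0.1099 and 0.1595 with zero, one and two events.
- Patients 34–45: 0.0309 × 0.0256 + 0.1099 × 0.1109 + 0.1595 × 0.3410 = 0.067.
- Total: 0.100 + 0.341 + 0.259 + 0.067 = 0.767.

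The stated death row is therefore too low by 0.005, 0.023, 0.054, 0.084, 0.106 and 0.115 across the six rates. No maximum N from 14 to 60 rescues it with the printed boundary; the closest is N = 31, with a largest error of 0.015.

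A numerical search over other nested boundaries found one distinct rule that matches all six cells: 2 events within 20 patients or 3 within 27. It gives 0.0923, 0.2014, 0.3233, 0.4441, 0.5550 and 0.6518. That rule is not in the documents. It ends at 27 patients (33 − 6, possibly phase II without the six carried over from phase I) and stops at 3 deaths, so it fits neither 45 nor the four-death sentence.

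**2. Non-hematologic boundary**

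| True rate | 0.40 | 0.44 | 0.48 | 0.52 | 0.56 | 0.60 |
|---|---|---|---|---|---|---|
| Stated | 0.099 | 0.194 | 0.339 | 0.522 | 0.707 | 0.854 |
| All printed rows | 0.432 | 0.509 | 0.609 | 0.724 | 0.833 | 0.918 |
| 1/1 dropped, 2/2 kept | 0.212 | 0.306 | 0.439 | 0.599 | 0.756 | 0.879 |
| 1/1 and 2/2 dropped | 0.099 | 0.194 | 0.339 | 0.522 | 0.707 | 0.854 |

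The stated row matches exactly, and only, with both rows dropped. At 40% the first patient contributes 0.400 of the 0.432. Expected patients treated at 40%, counting a crossing as final, are 26.7 with all rows and 42.2 without the two. At a 42% rate the stopping probabilities are 0.468 and 0.140.

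**The case against.** The arithmetic is not in dispute. The best counter-arguments concern its consequences.

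*The rules may start only in phase II.* Section 9.4 introduces them beside the expansion cohorts. If checks began at about the sixth or seventh patient, the non-hematologic rule would give 0.087 at 40% and 0.850 at 60%, close to the stated values. But Section 14.2 bases the rules on all 45 patients in both phases, and the pneumonitis/colitis row fits only with its 1/1 row active. Even on this reading, the 1/1 and 2/2 rows could never apply and should not be in the table.

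*A hold need not conflict with 3+3.* Enrollment could pause for review after patient 1 and the cohort could then expand. That is fair. The plan does not say so, however, and the table header speaks of stopping the trial.

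*Deleting 1/1 and 2/2 removes a safety trigger.* This stands as a real cost. DLTs count only in the first 28 days, while the stopping rules cover all treatment; some Grade ≥ 3 events are not DLTs; and the 4/4 row needs four events in four patients.

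*The intended death boundary is unknown.* This also stands. The four-death sentence appears word for word under pneumonitis/colitis too, where it does not belong, so text was copied between rules. Its agreement with the printed death boundary is weak evidence of intent.

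**Conclusion.** The point holds and is minor. The death row understates its printed boundary by up to 0.115: at a 10% death rate the chance of missing the problem is stated as 0.35 (1 − 0.652) and is 0.23 (1 − 0.767) for the boundary shown. The non-hematologic row describes a rule without two rows that the table tells staff to apply; with them, the false-stop probability at the acceptable rate is 0.432, not 0.099. The pneumonitis/colitis error is 0.005 in one cell and changes no decision.

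These figures assume independent patients with a constant event rate, all 45 treated unless the boundary is crossed, and a crossing counted as final. Using 45 is disclosed and is not an error. At every tabulated rate the printed boundaries are at least as likely to stop as the stated rows, apart from rounding, so patients are not less protected than stated. The Simon design for the primary endpoint is unaffected.

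**What to change.** In Section 14.2:

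1. **Death.** Confirm the intended boundary. If it is the printed one, replace the row with 0.097, 0.224, 0.377, 0.528, 0.661, 0.767. If it was 2 in 20 and 3 in 27, or another rule, correct the boundary table and the four-death sentence instead.
2. **Non-hematologic.** Either delete the 1/1 and 2/2 rows, which leaves the stated probabilities correct, or keep them, print 0.432, 0.509, 0.609, 0.724, 0.833, 0.918, and say how a hold after one event fits with the 3+3 expansion.
3. **Pneumonitis/colitis.** Change 0.092 to 0.097.
4. Label each row as calculated at the maximum N = 45, and remove the sentence about deaths from the pneumonitis/colitis rule.

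The cost is a rerun of an existing calculation, one confirmation and one decision; no patients are added. Deleting the two rows gives up an automatic hold on the first one or two patients. The 3+3 rule covers most of that gap in cycle 1, and the ongoing investigator review in Section 9.4 applies in the expansion. Related Grade ≥ 3 events that are late or do not count as DLTs in those first patients would then depend on clinical judgment.
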